4.4.2.7 Time to onset of 24 weeks CDP

This endpoint will be analyzed for patients in the ITT population. All 24-weeks CDP that occurred during the treatment period will be considered.

Patients without a 24-Week CDP will be censored at the last EDSS assessment. Patients who discontinue from the study due to lack of efficacy or death without confirmed progression of disease will be imputed as having an event at the time of discontinuation.

This endpoint will be analyzed using the same approach as described above in Section 4.4.2.6.

4.4.2.8 Time to onset of first new and/or enlarging T2 lesion

This endpoint will not be analyzed as the measurement of T2 lesion by MRI is only performed at week 24, 48 and 96, while the actual onset time can be very different from the MRI visit.

4.4.2.9 Time to onset of first T1 Gd-enhanced lesion

This endpoint will not be analyzed as the measurement of T1 lesion by MRI is only performed at week 24, 48 and 96, while the actual onset time can be very different from the MRI visit.

4.4.2.10 Total number of T1 Gd-enhanced lesions detected by brain MRI at Weeks 24, 48 and 96

The analyses will include patients in the ITT population. Data from unscheduled assessments will not be included in this summary or analysis.

The following analyses will be presented:

- Number and percentage of patients having 0, 1, 2, 3, and greater than 1 and greater than 3 lesions at weeks 24, 48 and 96.
- Number and percentage of patients having 0, 1, 2, 3, and greater than 1 and greater than 3 lesions in total detected at week 24, 48 and 96.
- The unadjusted and adjusted rates of lesion occurrence at weeks 24, 48 and 96 and the unadjusted and adjusted rate combining week 24, 48, 96 will be calculated:
 - The unadjusted rate will be the ratio of the total number of T1 Gd-enhanced lesions divided by the total number of interpretable MRI scans at each visit.
 - The adjusted rate will be derived using a negative binomial model. The dependent variable in the model will be the total number of T1-Gd-enhanced lesions. The model will be adjusted for the following covariates:
 - disease duration
 - presence of T1 Gd-enhanced lesions at screening (Yes/No),
 - presence of relapses prior screening as per CRF (Yes/No)
 - number of previous DMTs (1, >1).

In order to account for patients potentially receiving varying numbers of brain MRI scans during the study, the log-transformed number of brain MRI scans received will be included in the model as an “offset”.

- For the analysis above using negative binomial model for adjusted rate, if the model doesn't converge due to a high number of zero T1 Gd-enhanced lesion counts, other models, such as logistic regression model will be considered based on the same baseline variables. Patients having zero T1 Gd-enhanced lesions (but not missing) up to withdrawal will be considered as not having an event.

- Histogram of the count (0, 1, 2, 3, >1, >3) of T1 Gd-enhanced lesions at Weeks 24, 48 and 96, and during all visits (Weeks 24, 48 and 96) combined will be produced.

A descriptive analysis on the number of T1 Gd-enhanced lesions at screening and week 8 will also be performed.

4.4.2.11 Change in total T2 lesion volume detected by brain MRI from Week 8 to Week 96

The analyses will include patients in the ITT population.

Data from other unscheduled assessments will not be included in this summary or analysis.

Change and percentage change from week 8 in total T2 lesion volume detected by brain MRI will be summarized.

4.4.2.12 Volume and number of new and/or enlarging T2 hyperintense lesions at Week 24, 48 and 96

The analyses will include patients in the ITT population.

The number of new and/or enlarging T2 lesions at week 24, 48 and 96 will be calculated as the sum of the individual number of new and/or enlarging lesions at each visit. Data from other unscheduled assessments will not be included in this summary or analysis.

The volume of new/or enlarging T2 lesions will also be analyzed at week 24, 48 and 96.

The same analysis as total number T1-Gd enhanced lesions and will be provided for the number of new and /or T2 lesions and a summary descriptive will be provided for the volume of new/or enlarging T2 lesions.

4.4.2.13 Change in T1 hypointense lesion volume from Week 8 to Weeks 48 and 96

The analyses will include patients in the ITT population.

The volume of T1 hypointense lesions at week 8, 48 and 96 along with the change from week 8 to week 48 and to week 96 will be summarized descriptively. In addition, change and percentage change from Week 8 in T1 hypointense lesion volume detected by brain MRI at Weeks 48 and 96 will be analyzed using a longitudinal MMRM. These MMRM analyses will be undertaken using the same approach as described above in Section 4.4.2.3.

4.4.2.14 Percentage Change in brain volume from Week 8 measured at Weeks 24, 48 and 96

This endpoint will be analyzed on the ITT population.

Brain volume is recorded as an absolute “normalized” (refer to “Electronic Data File Format & Transfer Specifications”) value at week 8 (baseline reset) then recorded at subsequent visits as a percentage change relative to the normalized brain volume value

at week 8. Any volume measurement from the MRIs that were done after infusion at the same visit will not be included in the analysis, i.e., manually considering as missing. Same rule applies to cortical grey matter volume and white matter volume.

Percentage change in brain volume relative to Week 8, as detected by brain MRI scan, will be summarized at weeks 24, 48 and 96 using descriptive statistics. Data from other unscheduled assessments will not be included in this summary or analysis.

Descriptive statistics will be used to summarize the following:

- “normalized” and “pre-normalized” Brain volume at week 8
- percentage change in brain volume at weeks 24, 48 and 96

For the assessment of differences in the mean percentage change in brain volume at week 24, 48 and 96, a Mixed-Effect Model Repeated Measures analysis (MMRM) incorporating data collected up to 96 weeks of treatment will be used to assess all data collected over time with consideration of the variance–covariance matrix of the repeated measures. This method allows for a general unstructured variance–covariance matrix and will include data from patients with incomplete data from some scheduled time points.

The model will be implemented in SAS using the MIXED procedure and will include the percentage change at subsequent visits (weeks 24, 48 and 96) in brain volume as the dependent variable. The fixed effects in the model will include independent variables visit (nominal post - baseline visits at week 24, 48 and 96), along with the following covariates:

- normalized brain volume at week 8 (continuous variable),
- Duration since MS Symptom Onset (≤ 3 years, >3 and ≤ 5 years, >5 years and ≤ 10 years, >10 years),
- T2 volume at week 8 (continuous variable),
- presence of T1 Gd-enhanced lesions at screening (Yes/No)
- Number of previous DMTs (1, >1)

Visit will be treated as a repeated variable within a patient. Patient and visit will be treated as factor variables. An unstructured variance–covariance structure will be applied to model the within-patient errors. If the model doesn't converge, other variance–covariance structures can be considered. The model will be fitted using the Restricted Maximum Likelihood method (REML). Denominator degrees of freedom will be estimated using Satterthwaite's approximation.

Graphical presentations for least square means and 95% confidence intervals will be used to illustrate trends over time.

Sample SAS code can be found below (SAS code is regarded as “draft” until fully validated at the analysis stage):

```
proc mixed data=MRINBV method=REML;
  class VISIT USUBJID [covariates];
  model change = [covariates] VISIT / ddfm= satterthwaite;
  repeated VISIT / type=un subject = USUBJID;
  lsmeans VISIT /cl;
```

ods output lsmeans = lsm; * contains the adjusted means;
run;

4.4.2.15 Percentage Change in cortical grey matter volume from Week 8 measured at Weeks 24, 48 and 96

This endpoint will be analyzed on the ITT population. Note, this is an additional endpoint as compared with the protocol (refer to “Electronic Data File Format & Transfer Specifications”). Any volume measurement from the MRIs that were done after infusion at the same visit will not be included in the analysis, i.e., manually considering as missing.

Descriptive statistics will be used to summarize the following:

- “normalized” and “pre-normalized” cortical grey matter volume at week 8
- percentage change in cortical grey matter volume at weeks 24, 48 and 96

Data from other unscheduled assessments will not be included in this summary or analysis.

For the assessment of differences in the mean percentage change in cortical grey matter volume on MRI scans during the 96-week from week 24 up to week 96, an MMRM analysis will be undertaken using the same approach as described in Section 4.4.2.13, adjusting for covariates here will be as follows:

- cortical grey matter volume at week 8 (continuous variable),
- Duration since MS Symptom Onset (≤ 3 years, >3 and ≤ 5 years, >5 years and ≤ 10 years, >10 years),
- T2 volume at week 8 (continuous variable),
- presence of T1 Gd-enhanced lesions at screening (Yes/No).
- Number of previous DMTs (1, >1)

4.4.2.16 Percentage Change in white matter volume from Week 8 measured at Weeks 24, 48 and 96

This endpoint will be analyzed on the ITT population. Note, this is an additional endpoint as compared with the protocol (refer to “Electronic Data File Format & Transfer Specifications”). Any volume measurement from the MRIs that were done after infusion at the same visit will not be included in the analysis, i.e., manually considering as missing.

Descriptive statistics will be used to summarize the following:

- “normalized” and “pre-normalized” white matter volume at week 8
- percentage change in white matter volume at weeks 24, 48 and 96

Data from other unscheduled assessments will not be included in this summary or analysis.

For the assessment of differences in the mean percentage change in white matter volume on MRI scans during the 96-week from week 24 up to week 96, an MMRM analysis will

be undertaken using the same approach as described in Section 4.4.2.13, adjusting for covariates:

- white matter volume at week 8
- Duration since MS Symptom Onset (≤ 3 years, >3 and ≤ 5 years, >5 years and ≤ 10 years, >10 years),
- T2 volume at week 8,
- presence of T1 Gd-enhanced lesions at screening (Yes/No).
- Number of previous DMTs (1, >1)

4.4.2.17 Change from baseline in cognitive performance at Week 48 and Week 96 as measured by the BICAMS

This endpoint will be analyzed on the ITT population.

BICAMS analysis will be using three measures collected in the eCRF:

- The total number of correct symbols over 90 seconds recorded in the Symbol Digit Modalities Test (SDMT score)
- The total learning score from the California Verbal Learning Test (CVLT-II)
- The total learning score from the Brief Visuo-spatial Memory Test (BVMT-R)

These three measures will be summarized at each visit as the test value, the change from baseline and the % change from baseline values.

Additionally, the SDMT score analysis will be repeated for patients with no missing SDMT score at any visits. The BVMT-R score analysis will be repeated for patients with no missing BVMT-R score at any visits.

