#### **4.5.7 Brain Magnetic Resonance Imaging**

MRI will be used to monitor CNS lesions and potentially other pathophysiology, such as inflammation and neurodegeneration. Brain MRI scans will be obtained at study visits as shown in the Schedule of Assessments (see [Appendix 1](#)). All efforts should be made to obtain the brain MRI scans before the next ocrelizumab infusion and the scans should be reviewed locally for the presence of any non-MS pathology, including PML, before the next infusion is administered.

If patients receive corticosteroids for a treatment of an MS relapse, every effort should be made to obtain the scan prior to the first steroid dose if the pre-steroid scan is within 1 week of the scheduled visit. In patients already receiving corticosteroids for an MS relapse, there should be an interval of at least 3 weeks between the last dose of corticosteroids and the scan, to allow for normalization of blood-brain barrier.

MRI scans will be read by a centralized reading center for efficacy endpoints. Further details on scanning acquisition sequences, methods, handling, transmission of the scans, and certification of site MRI radiologist/technicians are described in a separate MRI technical manual.

Assessments will include T1-weighted scans before and after injection of gadolinium contrast, and may also include, but may not be limited to: fluid-attenuated inversion-recovery (FLAIR), proton density-weighted, and T2-weighted scans. The MRI activity will be based upon the MRI scan taken on week 8 when the drug has reached its anti-inflammatory activity.

The total brain volume and the different white and grey matter structures will be measured over the full duration of the study and follow-up period.

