4.4.4 Sensitivity Analyses

All analyses (binary endpoint, Kaplan-Meier, Life Table) listed for the primary endpoint in section 4.4.1 will be repeated for a modified protocol defined event definition, where any clinical MS relapses will contribute for a more comprehensive analysis of relapses as collected during the study.

For the primary endpoint, several sensitivity analysis will be performed:

- This analysis will be repeated for ITT population without imputation of missing values i.e. patients who discontinued treatment prior week 96, regardless of the reason, will be excluded from the analysis as their disease activity status cannot be ascertained.
- The analysis will also be repeated on the NEDA defined from MRI at screening visit instead of using MRI at week 8 as baseline. For this analysis, the number of new or enlarged T2 hyperintense lesion at week 24 visit will corresponds to the sum of the number of new or enlarged T2 hyperintense lesions at week 8 and 24.
- The analysis will also be repeated on the NEDA defined from MRI at week 8 as baseline and from protocol defined relapses occurred from Week 8 (only protocol defined relapses with study day \geq 57 will be considered).
- The analysis will be performed regarding the MRIs are done after infusion at the same visit. We will manually remove the measurement on T1 Gd-enhancing lesions from these MRIs if zero T1 Gd-enhancing lesions from these MRIs are reported, because the premedication corticosteroids potentially has impact on this MRI (Barkhof F, [Neuroradiology](#). 1994) We will impute the presence of T1 Gd-enhanced lesion based on those MRIs if there is no T1 Gd-enhancing lesions identified. We consider this is a more conservative way than the primary analysis.

To summarize, five sensitivity analysis will be performed for NEDA:

Sensitivity Analysis	Modification
A	No imputation of missing values, regardless of the discontinuation reason.
B	MRI baseline at screening (week 0)
C	Use clinical relapse not the protocol defined relapse in the definition.
D	Rebaseline relapse (PDR) from week 8 (exclude the relapses occurring in the first 8 weeks)
E	If the number of T1 Gd-enhanced lesion from the MRI that done after infusion equals zero, it will be imputed

Modified protocol-defined event definition

The definition of a modified protocol-defined event of disease activity is the occurrence of at least one of the following individual events while on treatment with ocrelizumab:

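### The secondary T1 Gd-lesion count has no rule for scans done after the infusion, although the SAP distrusts such readings elsewhere, so the Gd rate may be biased low at Weeks 24 and 48

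*SAP*

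**What the plan says.** - **Gd count (SAP 4.4.2.10).** The only stated data exclusion is "Data from unscheduled assessments will not be included in this summary or analysis". For the unadjusted rate it states: "The unadjusted rate will be the ratio of the total number of T1 Gd-enhanced lesions divided by the total number of interpretable MRI scans". The SAP does not say what makes a scan interpretable. For the adjusted negative binomial model, "the log-transformed number of brain MRI scans received will be included in the model" as the offset. If that model does not converge, the logistic fallback treats a patient with zero, non-missing lesions as having no event.
- **NEDA sensitivity analysis E (SAP 4.4.4).** For MRIs done at the same visit but after the infusion: "We will manually remove the measurement on T1 Gd-enhancing lesions from these MRIs if zero T1 Gd-enhancing lesions from these MRIs are reported". The reason given is "because the premedication corticosteroids potentially has impact on this MRI". A lesion is then imputed, and the SAP calls this more conservative than its primary analysis.
- **Volume endpoints (SAP 4.4.2.14 to 4.4.2.16).** "Any volume measurement from the MRIs that were done after infusion at the same visit will not be included in the analysis". The rule is extended to cortical grey matter and white matter. No reason is given.
- **Per-protocol set (SAP 4.1.3).** A post-infusion MRI excludes the patient. Repeating the primary and secondary analyses on this set is optional and depends on at least 10% of patients being excluded.
- **Protocol.** Section 4.3.3 gives 100 mg methylprednisolone before each infusion. Section 4.5.7 asks sites to try to scan ahead of the next infusion. In Appendix 1, on-treatment efficacy scans fall at Weeks 24, 48 and 96, and the infusions after the first dose at Weeks 24, 48 and 72. For patients already on steroids for a relapse, section 4.5.7 adds that "there should be an interval of at least 3 weeks between the last dose of corticosteroids and the scan".

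**The concern.** The SAP names a mechanism by which a post-infusion scan could show no enhancing lesion when one is present. It acts on that mechanism in one sensitivity analysis of a composite endpoint, but not in the endpoint that counts enhancing lesions directly. Gadolinium enhancement is the reading the SAP says the steroid may affect, so the Gd count is where a rule matters most.

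This is a single-arm study, so no control group carries the same measurement error. Any suppression passes straight into the reported rate, and it runs in the drug's favour. It also depends on the visit: Weeks 24 and 48 can be affected and Week 96 cannot. The by-visit rates and histograms planned in 4.4.2.10 could therefore show a pattern over time that comes partly from when patients were scanned.

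**Working it through.** The documents give no expected Gd rate, no number of post-infusion scans and no size of steroid effect, so there is no plan figure to reproduce. The check has three steps.

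**1. Does the text keep these readings?** Section 4.4.2.10 lists one exclusion, and it is not this one. The exclusion in 4.4.2.14 covers volumes and names its extensions; Gd counts are not among them. Analysis E is described as more conservative than the primary analysis, which implies that the default retains post-infusion zeros. The offset counts scans received. Only *interpretable* could imply an exclusion, and it is undefined and applies only to the unadjusted rate.

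**2. Direction and size.** Let λ be the true number of lesions per scan, f the share of scans at an infusion visit done after the infusion, and s the share of enhancing lesions hidden on those scans.

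- Expected rate at Week 24 or 48: (1 − f)λ + f(1 − s)λ = λ(1 − f·s). Relative bias is f·s, downward.
- Week 96: no infusion, so the rate is λ.
- Three visits combined, with equal scan numbers and equal λ: λ[2(1 − f·s) + 1]/3 = λ(1 − (2/3)·f·s).

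Both f and s are assumptions:

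| f | s | Bias at Week 24 or 48 | Ratio to true rate | Combined bias | Combined ratio |
|---|---|---|---|---|---|
| 1% | 0.25 | 0.25% | 0.9975 | 0.17% | 0.9983 |
| 5% | 0.5 | 2.5% | 0.975 | 1.7% | 0.9833 |
| 10% | 0.5 | 5% | 0.95 | 3.3% | 0.9667 |
| 20% | 1.0 | 20% | 0.80 | 13.3% | 0.8667 |

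**3. Which exclusion removes the bias?** Dropping every post-infusion scan from numerator and denominator leaves λ, a ratio of 1.00, provided scan timing is unrelated to lesion activity.

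Dropping only the zeros does not. Take a share q of scans truly positive, one lesion each, with s applied per scan. The numerator is (1 − f)q + f·q(1 − s) and the denominator (1 − f) + f·q(1 − s). With assumed q = 5%, f = 10% and s = 0.5:

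- Numerator: 0.045 + 0.0025 = 0.0475.
- Denominator: 0.9 + 0.0025 = 0.9025.
- Rate: 0.0475/0.9025 = 0.0526, a ratio of 1.05 to the true 0.05.
- Keeping all scans: 0.0475/0.05 = 0.95.

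A zeros-only rule would turn a rate 5% too low into one 5% too high. Over q from 2% to 10% and f from 2% to 10%, its ratio runs from about 1.01 to 1.05.

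**The case against.** The strongest reply is that the documents contain safeguards and that the effect may be negligible. The protocol asks for the scan before the infusion and for local review of that scan before dosing, so post-infusion scans should be uncommon. The per-protocol set removes affected patients. The SAP says only that steroids potentially affect the scan. The Gd count is a descriptive secondary endpoint in an exploratory, non-comparative study, with no decision attached. Analysing scans as read, with a conservative sensitivity analysis on the primary endpoint, is defensible.

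Much of this stands. It limits the size and rules out certainty. It does not close the gap: the SAP expects enough post-infusion scans to write rules for them, the per-protocol repeat is optional and conditional, and analysis E covers NEDA only.

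Three stronger readings are tempting and should not be drawn:

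- **That the 3-week interval condemns the premedicated scans.** It applies to steroids given for a relapse and is a scheduling instruction. It raises a separate, smaller gap: no SAP rule acts on a scan that breaches it.
- **That a patient given steroids for a relapse missing the protocol definition can pass as NEDA throughout.** Sensitivity analysis C counts any reported clinical relapse as an event.
- **That the volume exclusions show the SAP distrusts Gd readings.** No reason is given for them. The evidence on Gd is the statement in 4.4.4.

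**Conclusion.** The inconsistency is real. Followed as written, 4.4.2.10 keeps post-infusion Gd readings that 4.4.4 treats as doubtful, and it uses two differently worded scan sets for the unadjusted and adjusted rates. The Gd rate may be biased low at Weeks 24 and 48, and not by premedication at Week 96.

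A reader might infer that the rate is biased low by a known amount. The documents do not support that. The relative bias is f·s per affected visit and about (2/3)·f·s combined. Across the assumed values shown, it runs from 0.25% to 20% per visit and from 0.17% to 13.3% combined. The combined figure assumes equal scan numbers and equal true rates at the three visits. If no scans were done after the infusion, or steroids hid nothing, the bias is zero.

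**What to change.** In SAP 4.4.2.10:

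1. In the main analysis, set the Gd reading to missing for every scan done after the infusion at the same visit, whatever its count. Remove that scan from the numerator, the denominator and the offset. In the combined model this lowers the patient's scan count by one; in a by-visit model the patient drops out of that visit. SAP 4.7 already leaves missing values unimputed unless stated otherwise.
2. Define *interpretable* to match, and use the same scan set for the unadjusted rate and the model offset.
3. Show the all-scans result as a sensitivity analysis, and report the number of affected scans by visit.
4. Limit the rule to the Gd reading. Sections 4.4.2.12 and 4.4.3.5 borrow this analysis for T2 counts, which should not lose scans by accident.

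Separately, where steroid dates are available, add a sensitivity analysis of the Gd count that leaves out scans inside the Protocol 4.5.7 interval after relapse steroids. Concomitant medications are recorded, but SAP 4.4.3.6 uses relapse steroids only as yes or no, so check that last-dose dates exist.

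Do not remove zeros alone, and do not extend analysis E's imputation or the volume exclusions to the 3-week window. The first biases upward, and the documents give no analytic basis for the second.

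The cost is SAP wording. Analysis E and the volume rules already need the post-infusion flag. The downside is a few fewer scans and possibly a slightly less favourable Gd rate.

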### **6.4.4        Analysis Methods**

The analysis will be performed after the last CDP and CDI confirmation visit. The per-protocol population will be used for supportive efficacy analyses of the primary endpoint.

The evaluation of the clinical efficacy of ocrelizumab will be based upon the events in-between baseline visit and week 96. The MRI activity is evaluated from week 8 to week

96. The proportion of patients free from protocol-defined events up to Week 96 (i.e. patients with NEDA) will be calculated and the corresponding two-sided Clopper-Pearson 95% CI will be presented. Logistic regression models will be used to identify predictors of response to treatment (freedom from events). Variables that will be considered include: region, line of treatment (previous DMTs), gender, and baseline EDSS. In addition, specific efficacy endpoints, such as CDP, will be compared between patients with or without evidence of disease activity up to Week 96.

Details about the missing data handling, as well as sensitivity analyses, will be specified in the statistical analysis plan.

The proportion of patients free from a protocol-defined event up to Week 24, 48, and 96 will be calculated and the corresponding two-sided Clopper-Pearson 95% CI will be presented. Logistic regression models will be used to identify predictors of response to treatment (freedom from events). Variables that will be considered include: region, line of treatment (previous DMTs), gender, and baseline EDSS.

The annualized relapse rate by Week 96 will be analyzed using regression based on a negative binomial model, adjusting for factors that may include region, baseline EDSS (<4.0 vs  $\geq 4.0$ ), line of treatment (previous DMTs), with the log-transformed drug exposure time in years as an “offset” variable. The adjusted annualized relapse rate will be presented.

EDSS and its change from baseline, as well as other continuous variables such as the change in total T2 lesion volume and the key PROs, will be summarized descriptively at each assessment visit. The time course of these variables will be described using techniques such as linear mixed models for repeated measures (MMRM) adjusting for covariates such as the respective baseline score, geographical region, and baseline EDSS.

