4.4.2 Secondary Efficacy Endpoints

For all continuous secondary efficacy endpoints, in addition to the model based analyses, they will also be summarized descriptively at each assessment visit. Analysis populations are specified for each endpoint.

4.4.2.1 Proportions of NEDA patients during the initial 24-week and the initial 48-week period

This endpoint will be analyzed on the mITT population using the same approaches as described above in Section 4.4.1, for the proportion of NEDA patients assessed during the initial 24-week period and during the initial 48-week period.

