4.4.3 Exploratory Efficacy Endpoints

Exploratory efficacy endpoints include patient-reported outcomes (PROs) related to health-related quality of life (QoL), treatment satisfaction and other clinical endpoints. Summaries for change from baseline in these exploratory efficacy endpoints at Weeks 24, 48 and 96 will be provided.

In addition to the model based analyses, all PRO exploratory endpoints will be summarized descriptively at each assessment visit for individual question or domain as well as total scores as appropriate.

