4.4.3.1 Multiple Sclerosis Impact Scale (MSIS)-29

The MSIS-29 v2 is a 29-item PRO designed to measure the physical and psychological impact of MS. Items are rated on a 4-point likert scale and are summed for each domain. These summed scores are transformed for ease of interpretability. Lower transformed scores correspond to better HRQoL.

Domain	Items #	Item Scores	Domain score
--------	---------	-------------	--------------

Physical Scale	1-20	1 = Not at all 2 = A little 3 = Moderately 4 = Extremely	Sum of items 1-20, see below for missing data handling
Psychological Scale	21-29	1 = Not at all 2 = A little 3 = Moderately 4 = Extremely	Sum of items 21-29, see below for missing data handling

A transformed score will be calculated from each domain score, respectively

	Calculation for transformed score	Range
Physical Scale	$[(\text{domain score}-20)/(80-20)]*100$, see below for missing data handling	0-100
Psychological Scale	$[(\text{domain score}-9)/(36-9)]*100$, see below for missing data handling	0-100

Missing data handling:

- Respondents must have a minimum of 10 completed items in the physical scale, or a minimum of 5 completed items in the psychological scale in order to use the imputing process above to impute the missing individual items
- Missing scores in the specific scale are imputed as the average of the scores of all (completed) items in that scale. For example, if a patient has completed 15 items (item 1-15) in the physical scale and the values for item 16-20 are missing. Then first sum the completed items 1-15 and then divide by 15 to get his respondent-specific mean score. Then use this value as the score for each of the missing 5 items 16-20. Then generate a total score as usual by summing the values of the 15 completed items 1-15 and the 5 imputed items 16-20 based on the score calculation for physical scale above.

For any analyses of domain scores, transformed domain scores will be used as they have range of 0-100 and intuitive to understand.

A summary table will present, by visit, the number of patients with:

- All items completed in the physical scale
- A minimum of 10 completed items in the physical scale
- All items completed in the psychological scale
- A minimum of 5 completed items in the psychological scale

The mean change in the physical and psychological MSIS-29 v2 domain scores from baseline to weeks 24, 48 and 96 will be summarized descriptively.

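### T2 lesion volume, MSIS-29 and SymptoMScreen get only observed-case summaries in the SAP, although the protocol describes modelling them; Week 96 change looks too good if worsening patients leave more often

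*SAP*

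**What the plan says.** Protocol 6.4.4 groups EDSS with "other continuous variables such as the change in total T2 lesion volume and the key PROs, will be summarized descriptively at each assessment visit". It adds that their time course will be described using "techniques such as linear mixed models for repeated measures (MMRM) adjusting for covariates such as the respective baseline score".

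The SAP opens its secondary section (4.4.2) with: "For all continuous secondary efficacy endpoints, in addition to the model based analyses, they will also be summarized descriptively at each assessment visit". Its exploratory section (4.4.3) has a parallel sentence: "In addition to the model based analyses, all PRO exploratory endpoints will be summarized descriptively at each assessment visit". Both lead-ins presuppose models. The endpoint sections then differ:

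- **T2 lesion volume (4.4.2.11):** "Change and percentage change from week 8 in total T2 lesion volume detected by brain MRI will be summarized". No model follows.
- **MSIS-29 (4.4.3.1):** "The mean change in the physical and psychological MSIS-29 v2 domain scores from baseline to weeks 24, 48 and 96 will be summarized descriptively". The imputation rule there fills missing items within a form, not missed visits.
- **SymptoMScreen (4.4.3.3):** total score and its change are summarised descriptively, without imputation.
- **EDSS (4.4.2.3), T1 hypointense volume (4.4.2.13), and whole-brain, cortical grey and white matter volume (4.4.2.14 to 4.4.2.16):** each has an MMRM.

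SAP 4.7 leaves missing values unimputed unless a section says otherwise, and SAP 4 states that the SAP takes precedence over the protocol. As written, therefore, no model applies to the first three endpoints.

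**The concern.** An observed-case mean at Week 96 describes only the patients still assessed then. It represents the treated population only if leaving is unrelated to the score. The SAP itself does not assume this: for NEDA, relapse and progression, a patient who stops for lack of efficacy counts as having disease activity. In a single-arm study no control group shares the selective loss, and withdrawn patients are not replaced (Protocol 4.6.1).

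The SAP also accepts the remedy elsewhere: section 4.4.2.14 justifies the brain-volume MMRM partly because it uses patients with incomplete visits. T1 hypointense volume, from the same scans, is modelled; T2 volume is not. The SAP explains other departures, such as not analysing time to first T2 lesion (4.4.2.8), but not this one. At stake is whether reported Week 96 change in lesion load, quality of life and symptoms is flattering.

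**Working it through.** **The plan's own figure.** The precision statement is the only sizing figure. Exact Clopper-Pearson limits for 225/750 are 26.74% to 33.42%, half-width 3.34%; for 375/750 the half-width is 3.64%. These agree with the stated 26.7% to 33.4%, 3.3% and 3.6%. Nothing comparable is given for T2 volume or the questionnaires.

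**Inputs.** From the documents: N = 750 (SAP 2.3), two-sided 95% intervals (SAP 4), post-baseline visits at Weeks 24, 48 and 96. Dropout is not stated; the nearest figure is 3.5% stopping ocrelizumab for adverse events in the two earlier relapsing-MS trials (Protocol 1.2). Assumptions: dropout 5%, 10% or 20%; equal correlation of 0.5, 0.7 or 0.9 between changes at different visits; odds of leaving multiplied by 1.5 or 2.0 per SD of worsening.

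**Identity.** Let d be the fraction missing at Week 96, S the stayers' mean and L the leavers' mean (higher = worse). The mean for everyone is (1 − d)S + dL, so

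bias of the observed-case mean = S − [(1 − d)S + dL] = −d(L − S).

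If leavers are 0.5 SD worse and d = 0.10, the bias is −0.05 SD. If they are 1 SD worse and d = 0.20, it is −0.20 SD.

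**Simulation.** 600,000 patients per scenario, with dropout driven by the last observed change (missing at random, MAR). Observed-case bias at Week 96, in SD of change; negative means too favourable:

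| Correlation, odds per SD | 5% dropout | 10% | 20% |
|---|---|---|---|
| 0.5, 1.5 | −0.010 | −0.021 | −0.040 |
| 0.5, 2.0 | −0.017 | −0.035 | −0.069 |
| 0.7, 1.5 | −0.014 | −0.028 | −0.059 |
| 0.7, 2.0 | −0.024 | −0.048 | −0.096 |
| 0.9, 1.5 | −0.018 | −0.037 | −0.076 |
| 0.9, 2.0 | −0.031 | −0.062 | −0.122 |
| 95% half-width, 1.96/√[750(1 − d)] | 0.073 | 0.075 | 0.080 |

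The bias exceeds the half-width in only two cells, both at 20% dropout with odds of 2.0. In the check with odds of 1.0 (correlation 0.7, 10% dropout) the bias is 0.001, which is simulation error.

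**With the model.** The maximum-likelihood mean with unstructured covariance, which is what an unstructured MMRM estimates, has bias of at most 0.001 SD in every MAR scenario. If dropout instead depends on the unseen next value (not at random), the MMRM bias is −0.003 to −0.066 SD, against −0.015 to −0.129 SD for the observed-case mean.

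**The case against.** **The protocol does not fix MMRM.** A reader might infer that the SAP breaks a firm commitment. The protocol offers MMRM as an example, calls the analysis exploratory and mainly descriptive (section 6), and leaves detail to the SAP. That stands. But choosing no model is not a choice among techniques, and the SAP's own lead-ins still refer to models.

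**Cognition.** A reader might infer that BICAMS lost a model too. Protocol 6.4.4 does not name cognition. BICAMS is scheduled only at baseline, Week 48 and Week 96, and not at the early-discontinuation visit, so a patient who leaves before Week 48 has no post-baseline score for a model to use.

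**Size.** A reader might quote the bias as a percentage of the true change. That needs a true change the documents do not give. In one assumed case (0–100 score, SD 22, between-visit correlation 0.7, true change −3.0, about 12% dropout), the observed-case mean was −3.5 to −4.0. As a percentage this looks large, but it is 0.5 to 1.0 points. The SD of change is 22 × √[2(1 − 0.7)] = 17.0, and with 750 × 0.88 = 660 observed the 95% half-width is 1.96 × 17.0/√660 = 1.3 points. The calculations also use generic scores, not T2 volume data.

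**Other analyses exist.** Leavers count at earlier visits, summaries include medians and quartiles, SymptoMScreen has a proportion with limitation, and the number of new or enlarging T2 lesions has a negative binomial model. MRI and questionnaires are scheduled at early discontinuation. All true, but no rule brings those discontinuation values into the Week 96 change for these endpoints.

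**Baseline adjustment** adds little in a single-arm study. Agreed; the case rests on incomplete follow-up.

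**Conclusion.** The point holds for T2 lesion volume, MSIS-29 and SymptoMScreen: the protocol describes modelling T2 volume and the key PROs, the SAP presupposes models, and none is specified or its absence explained. The protocol does not define which PROs are key; these two are taken as the natural candidates.

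The bias is conditional. Under the assumed MAR dropout it is about 0.01–0.03 SD at 5%, 0.02–0.06 SD at 10% and 0.04–0.12 SD at 20%, always favourable, and zero if dropout is unrelated to the scores. At low dropout it is small beside sampling error; at about 20% with strong dependence it can exceed the interval's half-width. The documents do not support saying that the results will be biased, only that the planned analysis gives no protection.

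It would also go too far to carry the point to the primary endpoint, whose NEDA analysis has its own rules for patients who stop. The change is worth making before database lock because the SAP already contains the method.

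**What to change.** - Apply the MMRM of SAP 4.4.2.3 (visit, the endpoint's own baseline value, the same covariates, unstructured covariance, REML) to change in T2 lesion volume from Week 8, with Week 8 T2 volume as baseline; to the MSIS-29 physical and psychological scores; and to the SymptoMScreen total.
- Report least-squares means with 95% CI at the scheduled visits. Keep the observed-case tables as supportive, with the number observed at each visit.
- Optionally extend the model to SDMT and BVMT-R at Weeks 48 and 96 only, noting that patients who leave before Week 48 contribute nothing, so the gain is small.
- If the sponsor prefers summaries alone, state why and correct the lead-in sentences of 4.4.2 and 4.4.3.

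The cost is SAP wording, reuse of code already drafted and a few more model outputs. The limitation to state is that MMRM removes the bias only under MAR and merely reduces it otherwise.
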